#### 9.4 Study Design:

Describe study design in one to two sentences (e.g., prospective, use of existing records/data /specimens, observational, cross-sectional, interventional, randomized, placebo-controlled, cohort, etc.). Specify the phase – Phase I, II, III, or IV – for FDA-regulated investigational drug research

This study utilizes a single-blinded, randomized controlled non-inferiority trial design.

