1. Ketorolac Research Form: this form documents age, gender, pain location, inclusion criteria, exclusion criteria, objective adverse effects, and subjective adverse effects. No PHI or PII will be annotated on this form.
  1. Age will be documented in years only. The actual date of birth will not be documented.
  2. Gender will be documented as "M" for male or "F" for female. Or an appropriate box will be "checked" by the potential subject indicating subject gender.
  3. Pain location will be free text, but will be qualified and isolated to an anatomical region. This will be at the discretion of the investigator. For instance, "heel pain" would be annotated as foot pain, or "calf pain" as leg pain. The anatomical regions designated for the purposes of this research are: (1.) neck pain, (2.) shoulder pain, (3.) arm pain, (4.) elbow pain, (5.) forearm pain, (6.) wrist pain, (7.) hand pain, (8.) hip pain, (9.) thigh pain, (10.) knee pain, (11.) leg pain, (12.) ankle pain, (13.) foot pain or (14.) back pain.
  4. See inclusion and exclusion section in this document for a detailed description of both.
  5. Adverse events which occur due to administration of intramuscular ketorolac will be documented as objective and subjective adverse effects. [Note, "adverse events" is a phrase used to describe adverse events, reactions, and effects to intramuscular ketorolac.] Subjects will be provided a list of known adverse events occurring in greater than 1% of patients during the U.S. Food and Drug Administration (FDA) trials, according to the medical website UpToDate.com. The list of adverse events will be included on the Ketorolac Research Form. Subjects will be advised to circle any of the adverse events that they are experiencing. Each circled adverse event will count as 1 in a binary numbering system (1 indicating an adverse event and 0 indicating no adverse event) for purposes of analysis. Subjects may have more than one adverse event and each event will count as 1 point. The definitions of objective and subjective adverse event are provided below.

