#### Medication Administration

The primary investigator (PI) will maintain a resident-status through the Army-Baylor Doctor of Science Physician Assistant Studies Program for the entire research period of this study. The PI is a licensed physician assistant-certified and can under normal circumstances prescribe medication without approval by an attending physician. However due to the PI resident-status, all final treatment decisions (to include the ketorolac dosing used for this study) must be approved by a WBAMC ED attending provider.

For purposes of this study, the attending provider is usually a physician, but may be a physician assistant or nurse practitioner, and is the provider responsible for the subject's medical care at the time of data collection. Therefore, the attending provider is not a single individual. The PI may have a different attending provider for each shift or the attending may vary (being more than one individual) within one specific ED shift. Again, the attending provider is the final medical authority for every subject and it is the attending provider who will ultimately approve or disapprove ketorolac dosing regimens as they pertain to this study.

For instance, the PI may enroll and randomize a patient to the 15 mg ketorolac group. The PI will communicate this to the attending provider. However, the attending provider may reject the 15 mg dose and opt for a lower dose, higher dose or no ketorolac dose at all. For this reason, the inclusion and exclusion criteria for this study will document attending provider approval of the dosing regimen to which the patient is randomized prior to administration of the ketorolac.

The Regional Health Command Central (RHC-C) Human Research Protection Program was consulted on this issue specifically. Their guidance was that, for the purposes of this study, the attending physicians are not human subjects research in this study and do not require formal written consent to signify approval of the randomized ketorolac dose. However, they recommended that the PI obtain concurrence with the dose from the attending provider. The investigators for this study will have the attending provider sign the Ketorolac Research Form signifying their concurrence with the randomized dose.

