Study participants whose randomized dosing regimens are rejected by the attending provider will be excluded from the study. Again, attending provider concurrence with the randomized ketorolac dosing utilized in this study will be documented on the Ketorolac Research Form and is reviewed in the inclusion and exclusion portion of this application.

Prior to administration of ketorolac, a review of systems (ROS) will be performed with each patient to ensure that the subject has no medical history or other acute medical problems which would meet exclusion criteria for this study. However, this information will not be documented on any forms and will not be accessed through the EHR. The ROS is an anatomic or physiologic systems based detailed

interview with the patient to discuss their overall health and to identify any other medical issues that may or may not be connected with the patient's reason for ED visit.

The ROS used for this study is located within this application and will be located in the appendix of the manuscript when this study is complete. The study investigators' ROS may be separate from the actual attending provider ROS. The attending provider will perform their own ROS based on standard medical history taking. However, the ROS performed by the investigators for the purpose of this study will be used to discover any other medical issue or issues which may meet inclusion or exclusion criteria. If deemed pertinent to patient care, information obtained by performing the investigator ROS will be communicated verbally to the attending provider, so that they are aware that the patient may require evaluation for medical issues beyond an acute MSK injury or pain.

Ketorolac will be prepared for IM injection by the nursing staff assigned to the patient once the following have taken place:

1. Study subject has granted consent
2. Pregnancy is excluded
3. Breast feeding is excluded
4. Inclusion criteria are met
5. None of the exclusion criteria are met
6. The ROS is complete
7. The attending provider agrees to the randomized dose and formally prescribes the randomized dose of ketorolac through the EHR
8. Ketorolac will then be prepared for IM injection by the nursing staff assigned to the patient

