#### Secondary Outcome Variable Data.

The secondary outcome variables will be the number of subjects experiencing adverse events (both objective and subjective). This data will be provided by the subjects or observed, measured or verified by the investigators and will be documented on the adverse events section of the Ketorolac Research Form. Adverse events will be documented as objective and subjective adverse events. Subjects will be provided a list of the most common adverse events based on the medical website UpToDate.com. This list will be included on the Ketorolac Research Form. Subjects will be advised to circle any of the adverse events that they are experiencing. Each circled adverse event will count as 1 in a binary numbering system (1 indicating an adverse event and 0 indicating no adverse event) for purposes of analysis. Subjects may have more than one adverse event and each event will count as 1 point. The definitions of objective and subjective adverse event are provided below.

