**Descriptive Statistics Data.**

Descriptive statistics data will be gathered to find correlation between subject demographics (age and gender) and location and duration of pain. These data will be obtained on the Ketorolac Research Form which is completed by the subject and will be included as descriptive statistics only. The data may or may not be analyzed for statistical significance, this will be at the discretion of the statistician. Furthermore, data pertaining to subjects requiring analgesia beyond the ketorolac used for this study, will also be collected for descriptive purposes only. Furthermore, data pertaining to subjects requiring analgesia beyond ketorolac, will be collected for descriptive purposes only. The data will be collected on the Ketorolac Data Collection Workbook, along with the other data.

At the completion of the entire data collection period for the entire study, VAS measurements will be obtained based on the methodology above and all data pertaining to the primary outcome (VAS scores), secondary outcome (adverse events) and descriptive statistics (from the Ketorolac Research Form) will be transcribed on to a Microsoft Excel work sheet. Any PHI or PII at this point will be de-identified and only the Subject Study Number will be used for identification. All paper documents will be secured in a manner previously described. The Excel worksheet is located on the PIs government issued common-access-card protected laptop. Access to this laptop requires both a common-access-card and a personal identification number (PIN) assigned to that specific common-access-card. The worksheet will therefore be highly secure and saved to the hard drive of the PIs laptop. The hard drive on the computer can only be accessed by the PI (as previously discussed) and network system administrators with permission. The AI for this research may also have a copy of the de-identified data, however, the data will be stored and secured in the exact same manner as the PI (common-access-card and PIN protected). All measures will be taken to protect the information of the study, however no PHI or PII will be stored on the Microsoft Excel work sheet.

**10.3 At any point in the study, will you request, use, or access health information in any form, including verbal, hard copy and electronic?**

Yes  No

**10.4 Review the definitions below and respond to the following two questions. If you are not sure of the answers, email [contact] for assistance.**

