There is a very low risk for harm with participation in this study as the medication is being administered as recommended by the package insert and as recommended by the Food and Drug Administration. Furthermore, patients who are at increased risk for these adverse events will not be enrolled in the study, based on questions asked using the inclusion and exclusion criteria during the consent process. Ketorolac has the following known adverse events with applicable percent of patients who experience these effects: headache (17%), gastrointestinal pain (13%), dyspepsia (12%), nausea (12%), edema (4%), hypertension, dizziness (7%), drowsiness (6%), diaphoresis, pruritus, skin rash, diarrhea (7%), constipation, flatulence, gastrointestinal fullness, gastrointestinal hemorrhage, gastrointestinal perforation, gastrointestinal ulcer, heartburn, stomatitis, vomiting, anemia, prolonged bleeding time, purpura, increased liver enzymes, pain at injection site (2%), tinnitus, and renal function abnormality.

Additionally, there is a risk that the study subjects receiving the 15 mg dose will have inadequate pain control.

There is also the risk of accidental disclosure of protected health information (PHI) or personally identifiable information (PII). However, name and MRN will only be listed on the Master Key. The remainder of the research data will only have the Study Subject Number.

There are specific risks to pregnant and breastfeeding women. There is an FDA boxed warning that ketorolac is contraindicated in labor and delivery due to the potential to inhibit uterine contractions and adverse effects on fetal circulation. Additionally, ketorolac has a pregnancy risk factor of C. In this category, risk to the mother and fetus cannot be ruled out.

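### The form on which subjects circle adverse events carries a dose-coded study number and the attending's sign-off on the randomized dose, and nothing in the plan keeps the dose from the subject

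*Protocol*

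**What the plan says.** Section 9.4 of the protocol gives the design: "This study utilizes a single-blinded, randomized controlled non-inferiority trial design". Neither document says which party is blinded.

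Under Medication Administration in 10.1, the attending may accept or reject the assigned dose, and rejection excludes the subject. Acceptance is recorded by signature: "The investigators for this study will have the attending provider sign the Ketorolac Research Form signifying their concurrence with the randomized dose". The same subsection repeats that "attending provider concurrence with the randomized ketorolac dosing utilized in this study will be documented on the Ketorolac Research Form". On timing, it says that the eligibility criteria "will document attending provider approval of the dosing regimen to which the patient is randomized prior to administration of the ketorolac".

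The subject works on the same form. For age, gender, and location and duration of pain, 10.2 says: "These data will be obtained on the Ketorolac Research Form which is completed by the subject". For adverse events, the form description in 10.1 says: "The list of adverse events will be included on the Ketorolac Research Form". Section 10.2 adds: "Subjects will be advised to circle any of the adverse events that they are experiencing".

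Under Randomization and Study Subject Packet Creation, the Subject Study Number is built from K, then 15 or 60 for the dose, then a position number (the example is K15-30). It is written on the packet and on every document inside it. The VAS forms carry this number and nothing else that identifies the subject or treatment.

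**The concern.** If the subject is the blinded party, the paper that the subject handles has to be silent about the dose. Here the Ketorolac Research Form serves both as the record of the attending's dose approval and as the sheet on which the subject marks adverse events, and it bears a number that spells out the arm.

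This matters because pain is self-rated and the subjective adverse events are whatever the subject reports. The protocol also supplies an expectation for each arm. Section 14.1 warns that "there is a risk that the study subjects receiving the 15 mg dose will have inadequate pain control" and says that the drug's risks rise with dose; the consent process mentions possible inadequate pain control. A subject who knows the dose could report less relief on 15 mg, which would cost power on the primary test. A subject who knows it could also report more events on 60 mg, which would favour the claim that the lower dose has fewer adverse effects.

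**Working it through.** **Who can be blinded.** In 10.1 the investigator tells the attending the assigned group, the attending agrees to the dose and prescribes it, and nursing staff prepare and give it. The subject is the only one left. This is an inference, since 9.4 names no one.

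**What the subject can see, item by item.**

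| Item | On a form the subject handles? | Does it show the dose? |
|---|---|---|
| Subject Study Number | Yes: Research Form, VAS forms, packet | Yes, 15 or 60 is part of it |
| Attending's concurrence | Yes: Research Form | Not known; the form is not in the documents |

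The sequence is sign-off, then injection, then assessment at 30 and 60 minutes. The signature is therefore already in place when the subject circles post-dose events. No step covers, detaches or withholds it.

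**The plan's own figure.** Inputs from 11.5: margin 13 mm, SD 27, true difference 0, one-sided alpha 0.05, 55 per arm.

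- SE = 27 × √(2/55) = 5.15 mm; critical t on 108 df = 1.659.
- Non-centrality = 13/5.15 = 2.52; non-central t power = 80.6%. The stated 80% is reproduced.

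**Illustration for pain.** The documents give no figure for an expectation effect, so the shifts are assumed. Suppose that the doses are truly equal but 15 mg subjects report *b* mm less relief. The non-centrality becomes (13 − *b*)/5.15.

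| *b* (mm, assumed) | Non-centrality | Power |
|---|---|---|
| 0 | 2.52 | 80.6% |
| 2 | 2.14 | 68.4% |
| 3 | 1.94 | 61.2% |
| 5 | 1.55 | 46.0% |

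**Illustration for adverse events.** Assume a true rate of 20% in both arms, 55 per arm, and over-reporting on 60 mg only. Exact binomial enumeration gives the chance of declaring fewer events on 15 mg. The one-sided z-test is that of protocol 11.6. The SAP names Fisher's exact test without stating sidedness, so both versions are shown.

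| Reported rate, 15 mg vs 60 mg | One-sided z | Fisher, one-sided | Fisher, two-sided |
|---|---|---|---|
| 20% vs 20% | 4.8% | 3.0% | 1.4% |
| 20% vs 25% | 15.2% | 10.7% | 5.9% |
| 20% vs 30% | 33.4% | 25.9% | 16.7% |

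The two-sided column counts only significant results in favour of 15 mg. The direction is the same under every test, but the size depends on the test and on the assumed shift.

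**The case against.** The strongest reply concerns the sign-off. A reader might infer that the subject would see the dose even with neutral study numbers, because a signature agreeing to a dose needs the dose written beside it. The documents do not support that. The form's listed contents in 10.1 (age, gender, pain location, eligibility criteria, adverse effects) include no dose field. The concurrence criterion in 12.5 refers to intramuscular ketorolac and gives no dose. The investigator tells the attending the assignment, and the order goes through the electronic record, so a bare signature against a neutral number could document agreement without revealing the arm. Nor is the Research Form said to be a single page, as the VAS forms are. Parts of it are completed by the investigator, and the signature may sit on a page that the subject never handles. All of this stands, and it limits the sign-off to a possible route.

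Three further limits also stand. The VAS is marked on separate forms, so the primary outcome is exposed through the study number and only indirectly through the Research Form. The expectation that the protocol creates works against 15 mg on pain, so it lowers power and does not manufacture non-inferiority. Objective adverse events are observed by the investigator, so subject expectation bears mainly on the subjective ones.

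The reply does not remove the study number. It shows the dose on every packet document, and no procedure hides it. Correcting the number alone would also leave a gap: because the attending may reject a particular dose, the approval has to be tied to a dose somewhere, and the plan does not say that this will be done out of the subject's view.

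**Conclusion.** The point holds in this form. The plan puts a dose-coded number and a dose sign-off on a form that the subject completes in part after the injection, and says nothing about keeping the dose from the one party who could plausibly be blinded. The number is a demonstrated leak. The sign-off is a possible second one that cannot be confirmed without the form.

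The size of any bias is not known. The percentages above rest on assumed reporting shifts, an assumed 20% event rate and 55 evaluable subjects per arm, and none of them can be assigned to the signature as distinct from the number. They show that modest shifts would matter: a 3 mm shift takes power from 81% to 61%, and 5 points of over-reporting on 60 mg raises the false claim of fewer events on 15 mg from 5% to 15% under the z-test, or from 3% to 11% under a one-sided Fisher test. The change is worth making because it is cheap and protects self-reported outcomes, not because a bias of any given size has been shown.

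**What to change.** In protocol 9.4 and 10.1:

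1. Name the subject as the blinded party.
2. Replace the K15/K60 numbering with neutral Subject Study Numbers, linked to the arm only on an allocation sheet.
3. Record the attending's concurrence with the randomized dose on that allocation sheet, kept out of the subject's packet.
4. State that everything the subject handles (Ketorolac Research Form, VAS forms, packet cover) carries no dose, no dose sign-off and no dose-coded number.

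Steps 2 and 3 belong together: moving the signature alone would leave the coded number in view, and changing the number alone could lead to the dose being written beside the signature.

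The cost is one extra page per subject, a lookup step when the dose is ordered, and a few sentences of text. The check that the present numbering gives against dosing the wrong arm moves to the allocation sheet. Concurrence is still documented for audit, and the attending's authority over treatment is unchanged.

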#### Randomization and Study Subject Packet Creation

Fully enrolled subjects will be randomized based on a two block randomization generated by the website [www.graphpad.com](http://www.graphpad.com). Randomization will be created so there are two groups (two block randomization), one which will receive 15 mg of intramuscular ketorolac and one which will receive 60 mg of intramuscular ketorolac. Each group (block) will consist of 61 subjects per the power analysis described later in this document and will be assigned a Subject Study Number.

The Subject Study Number will be comprised of a "K" for ketorolac, "15" or "60" designating which dose of ketorolac will be administered and then a specific number reflecting their position within the randomization block (randomization block number). For instance, a Subject Study Number of "K15-30" would signify that this patient was randomized into the ketorolac 15 mg group and the number 30 would reflect both the block to which the patient was randomized and confirm that the patient is indeed in the 15 mg group. Using both "15" or "60" and the randomization block number acts as a checks and balance to ensure that the patient is randomized into the correct group, and that the subject receives the correct randomized dose. Based on the randomization block number it is possible to know into which group the subject was randomized, the dose of ketorolac which will be administered and the order of the patient in the overall randomization. Following randomization, Subject Study Packets will be prepared.

Subject Study Packets will be prepared prior to the data collection (prior to the screening process). These packets will be created using manila envelopes capable of containing all study documents and which can be sealed. The contents of the envelopes will include the (1.) Ketorolac Research Form, (2.) Informed Consent Form (which includes consent for a POC UHCG), (3.) HIPAA Authorization Form, (4.) pretreatment VAS form, and two post-treatment VAS forms. None of the documents utilized or created throughout the study will be entered in to the subjects EHR. The manila packet and all documents contained within it will be annotated with the Subject Study Number (as described above). A description of these forms is listed below.

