All appropriate provider and nursing policies, safeguards and regulations governing the preparation and administration of parenteral medication within the WBAMC ED will be followed and standard of care for the injection of ketorolac will not be altered, omitted or deviated from industry, ethical, moral or hospital standards. The investigators will not have any part in preparation or administration of the ketorolac-this will be completely handled by WBAMC ED nursing staff and the order for the ketorolac will have already been approved and prescribed by the WBAMC attending ED provider through the EHR.

As the medication is prepared for administration, the investigator will educate the subject on the use of the VAS and annotate their pre-treatment pain score on the VAS form. For the purposes of this study, the VAS is a validated tool that will be used to objectively measure the subject's response to ketorolac.

The subject will then be injected intramuscularly with the dose of ketorolac randomized to the patient based on the Subject Study Number assigned to the randomized packet, which was assigned to that subject. Again, all appropriate provider and nursing policies, safeguards and regulations governing the preparation and administration of parenteral medication within the WBAMC ED will be followed and standard of care for the injection of ketorolac will not be altered, omitted or deviated from industry, ethical, moral or hospital standards.

Following the administration of ketorolac and at the 30 and 60 minute intervals, VAS scores will be recorded, the patient will be assessed for adverse effects (objective and subjective) and blood pressure and heart rate measurements will be taken. At the conclusion of the 60 minute period and documentation of the VAS and any adverse effects, the data collection phase will be considered complete. The subject will be notified that the study has concluded. The attending provider will then continue with evaluation, treatment, and disposition, as indicated.

As outlined during the consent process, additional analgesia will be available during the course of the study. The decision to provide additional analgesia will be made by the attending provider in consideration of the study subject's clinical scenario. Study subjects who receive additional analgesia will be unenrolled from the study at the time of administration of the additional analgesia.

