**11.5 Please provide a justification for your sample size**

In this study, we assume that we are comparing the mean VAS between the 2 Groups, and the margin of non-inferiority is -13 mm. The actual difference between the means is assumed to be 0 and the standard deviation is assumed to be 27 for the 2 Groups (estimated from the Motov manuscript). Group sample sizes of 55 and 55 achieve 80% power to detect non-inferiority using a one-sided, two-sample equal-variance t-test with alpha of 0.05. The sample size per arm was increased from 55 to 61 to account for an anticipated 10% dropout or withdrawal of subjects (5.5 subjects was rounded to 6 subjects).

**11.6 Data Analysis Plan: Complete description: Background, Objectives, Design, Step by Step how the project is going to be done, Data analysis plan:**

To test for non-inferiority of dose 15mg to dose 60 mg using the VAS pain score, the analysis to be used is called an interval test. The hypothesis will be tested using the construction of one-sided confidence intervals or one-sided, two-sample equal-variance t-test with alpha of 0.05. To test that the lower dose has less adverse effects, we will use the one-sided z-test for testing two independent proportions. All tests will be conducted at the 0.05 level of significance.

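### The attending may refuse the allocated dose after randomisation, knowing the arm, and refused subjects are excluded, so exclusion can differ by arm and leaves no primary outcome for them

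*Protocol*

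**What the plan says.** The order of events comes from two parts of Protocol 10.1.

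- **Randomization and Study Subject Packet Creation:** "Fully enrolled subjects will be randomized based on a two block randomization". The Subject Study Number carries the dose and appears on the packet and every form in it. The position number shows the arm as well: "Based on the randomization block number it is possible to know into which group the subject was randomized".
- **Medication Administration, disclosure and refusal:** once a subject is allocated, "The PI will communicate this to the attending provider". In the protocol's own example, "the attending provider may reject the 15 mg dose and opt for a lower dose, higher dose or no ketorolac dose at all". The consequence is stated directly: "Study participants whose randomized dosing regimens are rejected by the attending provider will be excluded from the study".
- **Medication Administration, order of steps:** the seventh item before injection is "The attending provider agrees to the randomized dose and formally prescribes the randomized dose of ketorolac through the EHR"; the eighth is drug preparation. While the drug is being prepared, the investigator is to teach the VAS and "annotate their pre-treatment pain score on the VAS form". The later scores follow at 30 and 60 minutes after the injection.

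Three places deal with the attending's concurrence, and they differ. Section 12.5 asks for agreement to intramuscular ketorolac and names no dose. Section 14.1 makes agreement to the dosage regimen a condition of enrolment. Section 10.1 obtains agreement to the dose after allocation, while saying that the eligibility criteria cover it.

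Section 13.6 plans a record of withdrawals and exclusions. The attending also signs the Ketorolac Research Form for the dose. Neither document commits to reporting refusals by arm. Protocol 11.1 to 11.6 and the SAP name no analysis of all randomised subjects.

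**The concern.** Randomisation makes the arms comparable at the moment of allocation. Here a person who knows the allocation then decides who stays. If the patients refused at 15 mg differ in expected pain relief from those refused at 60 mg, the remaining groups are no longer the groups that were randomised.

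The documents supply reasons that could act on each arm. Section 9.2 gives 30 mg and 60 mg as the common intramuscular doses. Section 14.1 names a risk of inadequate pain control at 15 mg and says that risks rise with dose. A refusal is therefore plausible in either arm, for different reasons and in different patients.

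The direction matters in a non-inferiority trial. If the subjects refused at 15 mg would have had less relief, removing them flatters the low dose and makes a false claim of non-inferiority more likely. If they would have had more relief, power falls. The adverse-event comparison is exposed in the same way. Because no post-treatment scores are scheduled for refused subjects, an as-randomised analysis cannot be rebuilt later from planned data.

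**Working it through.** **Inputs from the Protocol (11.2 to 11.6).** One-sided two-sample equal-variance t-test, alpha 0.05; margin 13 mm; SD 27 mm; true difference 0; 55 evaluable and 61 enrolled per arm.

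**Inputs assumed, because the documents do not give them.** The refusal fraction f, and the gap d in mean VAS reduction between kept and refused subjects.

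**1. The plan's own figure.** SE = 27 × √(1/55 + 1/55) = 5.149 mm, and the noncentrality is 13/5.149 = 2.525. With 108 df and critical value 1.659, power is 0.806; at 54 per arm it is 0.7998. So 55 is reproduced. The allowance is 55 × 1.10 = 60.5, rounded to 61, and is stated as being "to account for an anticipated 10% dropout or withdrawal of subjects"; refusal of the dose is not mentioned. With all 61 per arm analysed, power is 0.841.

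**2. What data a refused subject has.** Agreement is step 7, preparation is step 8, and the pre-treatment form is marked during preparation. The 30 and 60 minute scores are timed from the injection. Neither post-treatment score is therefore scheduled for a refused subject, and the change from baseline (11.1) cannot be computed. The baseline is less clear. The 20 mm entry criterion (12.5) must be met at step 4, so some earlier pain rating is implied, but no place to record it is described, and 10.2 defers all VAS measurement until data collection ends.

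**3. Refusals in the 15 mg arm only.** Removing a fraction f whose mean differs by d moves that arm's mean by f × d. False non-inferiority is the noncentral-t probability of passing when the true difference is −13 mm, with noncentrality shift/SE. If the shift runs the other way, power at a true difference of 0 uses (13 − shift)/SE. Example: f = 5% of 61 is about 3, leaving 58 v 61. SE = 27 × √(1/58 + 1/61) = 4.952; shift = 0.05 × 20 = 1 mm; noncentrality = 1/4.952 = 0.202, which gives 0.074.

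| f, d (assumed) | Shift | Analysed, 15 v 60 mg | False non-inferiority | Power, opposite shift |
|---|---|---|---|---|
| none | 0 | 61 v 61 | 0.050 | 0.841 |
| 2%, 10 mm | 0.2 mm | 60 v 61 | 0.054 | 0.828 |
| 5%, 20 mm | 1 mm | 58 v 61 | 0.074 | 0.778 |
| 10%, 20 mm | 2 mm | 55 v 61 | 0.106 | 0.703 |

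If the 10% allowance is already spent (55 per arm before refusals), the last three rows become 0.054/0.792, 0.073/0.738 and 0.102/0.665, against 0.050/0.806 with no refusals.

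**4. Refusals in both arms.**

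- 10% in each arm with the same gap: shift 0, false non-inferiority 0.050.
- 10% v 5% with a 20 mm gap: 2 − 1 = 1 mm; 55 v 58 gives 0.074.
- 5% in each arm with 10 mm gaps in opposite directions: 0.5 + 0.5 = 1 mm; 58 v 58 gives 0.074.

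Equal refusal rates therefore cancel only if the same kind of patient is refused in each arm.

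**The case against.** The strongest reply is that refusals may hardly occur. Section 12.1 admits only patients whom the attending would routinely treat with intramuscular ketorolac, 13.3 restricts entry to ESI 4 or 5, and 14.6 describes both doses as in very common use. At 2% refusal and a 10 mm gap, false non-inferiority is 5.4%. The 10.6% case needs 10% refusal in one arm only and a 20 mm gap, which is more than one and a half times the margin. This stands, and it limits the severity. It does not remove the point, because none of those passages screens on acceptance of both doses.

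A second reply is that planned paperwork could already show refusals by arm: the signed Ketorolac Research Form bears the arm-coded number, and 13.6 adds an exclusion record. This also stands. What is missing is a commitment to report them.

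A reader might infer three stronger things that the documents do not support. One is that exclusion does differ by arm, or that it favours 15 mg; no rate or direction is given, and the 15 mg refusal in 10.1 is only an example. Another is that a refused subject has no pain rating at all; the entry criterion implies one, and only the 30 and 60 minute scores are clearly absent. The third is that randomisation has ceased to protect the comparison; with rare refusals, or similar refusals in both arms, the effect is small or nil.

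Removals for other reasons, such as additional analgesia, are a separate matter and add no weight here.

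**Conclusion.** The structure is explicit: allocation, disclosure to the attending, possible refusal, exclusion. Nothing in Protocol section 11 or the SAP repairs it. Exclusion can therefore differ by arm, and the primary outcome is not obtainable for refused subjects from planned data.

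The size is unknown. Under the assumed inputs, false non-inferiority runs from 5.4% to 10.6% against a nominal 5%, or power falls to between 0.83 and 0.70 from 0.84 if the shift goes the other way. Those figures rest on the plan's SD of 27 mm and margin of 13 mm, on refusals in the 15 mg arm only, and on 61 per arm with no other loss.

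Confidence is high on the sequence and low on size and direction. The point should be fixed because the remedy is cheap and most of the exposure is avoidable. The evidence does not support a higher grade. The differing concurrence passages need reconciling whatever the size of the bias.

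**What to change.** **Main change.** Before the allocation is revealed, record that the attending responsible for the subject accepts either study dose for this patient. Use a screening form kept outside the numbered packet, since the packet number shows the arm. Make this the criterion in 12.5, and bring 10.1 (both subsections), 12.5 and 14.1 into the same order. The attending's clinical authority after allocation stays as it is.

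**For any subject still refused after allocation,** for example because the attending changes within a shift:

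- Collect baseline, 30 and 60 minute VAS where the subject agrees, and define the time origin for subjects not given the allocated injection.
- Report refusals by arm with reasons, from the 13.6 record and the Ketorolac Research Form.
- In the SAP, present all randomised subjects with outcome data in their assigned arm beside the treated-as-allocated analysis, and say that this mitigates the bias only in part. For example, if 10% of the 15 mg arm switch to 60 mg when the true difference is 13 mm, the as-randomised contrast still moves by 0.10 × 13 = 1.3 mm, which gives about 8% false non-inferiority at 55 per arm.
- Do not require both analyses to agree unless the power cost is stated. In one simulated scenario (55 per arm, 10% refused and switched to 60 mg, refused subjects 20 mm better), power was about 0.65 under that rule against 0.79 for the as-randomised set alone.

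**Cost.** One more screening form, a few extra VAS forms and a short SAP paragraph. Patients acceptable for only one dose are not enrolled, which may slow accrual and slightly narrow the population.

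**If enrolment is complete,** as the SAP's mention of a choice made during analysis may suggest, report refusals by arm and add a sensitivity analysis over assumed outcomes for the refused subjects.
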